### **3.3. Exclusion Criteria**

A subject will not be eligible for inclusion in this study if any of the following criteria apply during screening:

1. Soft tissue sarcomas with biology or defined treatments for which pazopanib is not indicated, including adipocytic STS, gastrointestinal stromal tumors (GIST), or Kaposi's sarcoma.
2. Previously received an mTOR inhibitor or angiogenesis inhibitor.
3. Known active uncontrolled or symptomatic central nervous system (CNS) metastases. A subject with controlled and asymptomatic CNS metastases may participate in this study. As such, the subject must have completed any prior treatment for CNS metastases  $\geq 28$  days (including radiotherapy and/or surgery) prior to start of treatment in this study and should not be receiving chronic corticosteroid therapy for the CNS metastases.
4. Subjects with hemoptysis, central nervous system hemorrhage, or gastrointestinal hemorrhage within the last 6 months prior to treatment are excluded due to pazopanib-associated risk of bleeding.
5. Subjects with severe hepatic impairment and active gastrointestinal bleeding.

6. Uncontrolled serious medical or psychiatric illness.
7. Subjects with a currently active second malignancy other than non-melanoma skin cancers, carcinoma in situ of the cervix, resected incidental prostate cancer, or other adequately treated carcinoma-in-situ are ineligible. Subjects are not considered to have a currently active malignancy if they have completed therapy and are free of disease for  $\geq 1$  year).
8. Recent infection requiring systemic anti-infective treatment that was completed  $\leq 14$  days prior to enrollment (with the exception of uncomplicated urinary tract infection or upper respiratory tract infection).
9. No clinically significant gastrointestinal abnormalities including malabsorption syndrome, major resection of the stomach or small bowel that could affect the absorption of study drug, active peptic ulcer disease, inflammatory bowel disease, ulcerative colitis, or other gastrointestinal conditions with increased risk of perforation, history of abdominal fistula, gastrointestinal perforation, or intra-abdominal abscess within 28 days prior to beginning study treatment.
10. Uncontrolled diabetes mellitus as defined by HbA1c  $>8\%$  despite adequate therapy.
11. Subjects with unstable coronary artery disease, myocardial infarction, or an arterial thromboembolic event during preceding 6 months.
12. Subjects with history of interstitial lung disease and/or pneumonitis, or pulmonary hypertension.
13. Use of strong inhibitors and inducers of CYP3A4 within the 14 days prior to receiving the first dose of nab-Sirolimus. Additionally, use of any known CYP3A4 substrates with narrow therapeutic window (such as fentanyl, alfentanil, astemizole, cisapride, dihydroergotamine, pimozide, quinidine, terfenadine) within the 14 days prior to receiving the first dose of nab-Sirolimus.
14. Active Hepatitis B or Hepatitis C infection.
15. Systemic immunosuppression, including HIV positive status with or without AIDS.
16. Subjects with history of intestinal perforations, fistula, hemorrhages and/or hemoptysis  $\leq 6$  months prior to first study treatment
17. Subjects with hypercholesterolemia receiving ongoing treatment with simvastatin.
18. Subjects who have had major surgery within 28 days of planned initiation of protocol therapy, or subjects who have/have had wound dehiscence, or other open wounds (including diabetic or infectious wounds) with active wound complications.
19. Subjects with prior history of severe hypersensitivity (Grade 3 or higher) to any known drug excipients, including anaphylaxis to human serum albumin.
20. Subjects with uncontrolled hypertension, defined as an average SBP  $\geq 140$  mmHg or an average DBP  $\geq 90$  mmHg despite best supportive care measures.

**4. TABLE OF EVENTS**

The schedule of assessments in Table 4 and Table 5 outline the specific time points for study assessments.

**Table 4. Schedule of Assessments (Day 1 and Day 8 Dosing – Subjects enrolled under Amendment 2, v3.0 or earlier)**

Assessments a	Baseline Screening b	Treatment Phase 21-day (3-week) Cycles Days			End of Treatment (EOT) Visit d	30 Day Follow-Up Visit (+/- 7 days)	Follow-up Q12W after last visit till study closes or withdrawal of consent – via phone call
		1	8	15 c			
Informed Consent	x						
Medical History/Demographics	x						
I/E Criteria	x						
HIV, HBV sAg, HBV cAb, HCV Ab	x						
Urinalysis	x	x			x		
TSH, T3, T4 e	x						
Optional Biomarker f	x						
Pregnancy Test g	x				x	x	
LVEF (echocardiogram or MUGA)	x					x	
12-lead electrocardiogram h	x	x h					
Physical Exam	x	x	x	x	x	x	
Vital Signs, height, and weight i	x	x	x	x	x	x	
Prior / Concomitant Medications and Procedures	x	x	x	x	x	x	
CBC/Differential	x	x	x	x	x	x	
Chemistry Panel	x	x	x	x	x	x	
Lipid Panel h	x h	x h					
Rapamycin level j		x j	x j	x j			
ECOG performance status	x	x	x	x	x	x	
CT k	x	Every 6 weeks for the first year, then every 12 weeks					
nab-Sirolimus infusion l		x	x				
Pazopanib m		Daily					
Adverse Event Assessment		Continuous from time of consent to 30 days after last study drug					
Survival Assessment							x

a All visits are allowed to occur in a window of  $\pm 3$  days unless otherwise specified.

b Baseline screening visit will be done within 28 days prior to study treatment Day 1. Baseline scans should be completed within 28 days of C1D1, as close to C1D1 as possible.

c Day 15 visit is only in Cycle 1 and 2. Cycle 3+ does not have a Day 15 visit.

d End of Treatment-phase (EOT) Visit should be within  $\pm 3$  days of last study treatment.

e Thyroid function test to be repeated as needed, based on investigator's opinion.

f Subjects who consent for pre-treatment tissue collection for biomarker analysis: either fresh-frozen or formalin-fixed paraffin-embedded (FFPE) tumor blocks or unstained slides (min 10). Fresh tissue collection may only be obtained if clinically feasible and without undue risk to the subject.

g For all female subjects of childbearing potential (see Inclusion 5), a serum pregnancy test will be done at screening. A serum or urine pregnancy test will be repeated within 72 hours before first treatment if the serum pregnancy test occurred  $>72$  hours before dosing, and at EOT and 30-Day Follow-Up (if applicable). Pregnancy tests conducted after screening will be recorded in the source documentation only.

h Single tracing ECG and lipids evaluations are every even cycle (C2, C4, C6, etc.). Only lipid panel at baseline is required to be fasting lipid.

i Height is measured only at C1D1. BSA is calculated ONLY on C1D1; to be recalculated only if the weight changes by  $> 10\%$  in subsequent cycles, at which point the recalculated weight will become the new baseline. Vitals signs to include respiration rate, temperature, systolic/diastolic blood pressure, and pulse. Vital signs to be collected Pre-Dose (within 15 minutes prior to start of infusion) and Post-Dose (+10 minutes from end of infusion).

j Rapamycin levels are done locally and for all subjects in Phase 1 at Cycle 1 D8 prior to infusion (within 15 minutes prior to infusion) and on D15 (any time) to assess trough levels as well as in Cycle 2, D1 and D8 prior to infusion and on Day 15 (anytime).

k Baseline scans should be done within 4 weeks of C1D1, preferably as close to first treatment as possible. Every 6 weeks from C1D1 ( $\pm 1$  week) for the first year, then every 12 weeks ( $+/- 1$  week) until disease progression or last treatment, regardless of missed or out of window doses. End of Treatment Visit CT/MRI should be performed only for those subjects that discontinue treatment for a reason other than disease progression. All responses must be confirmed by an additional CT scan after 6 weeks. MRI may be used if CT is contra-indicated for a subject. The same mode of imaging at screening must be used consistently throughout the study.

l Nab-Sirolimus must be administered after all study specific assessments are done in a visit. Pazopanib dosing is daily and oral and may be dosed anytime in relation to ABI-009 administration. Nursing supervision or documentation of pazopanib dosing on days where nab-Sirolimus is administered is not needed. See Section 6.2 for pazopanib dosing, schedule, and administration. Vital signs to be collected Pre-Dose (within 15 minutes prior to start of infusion) and Post-Dose (+10 minutes from end of infusion). There is a 60-minute observation window post end of infusion for Cycle 1. If a subject completes Cycle 1 with no infusion related reactions, the observation period may be omitted for Cycle 2 and onwards. If at any time the subject experiences an infusion related reaction, the 60-minute post-dose observation period will be reinstated.

m Subjects will complete daily drug diary when receiving pazopanib, to be reviewed on Day 1 of each cycle.

**Table 5. Schedule of Assessments (Day 1 Only Dosing – Subjects Enrolled under Amendment 3, v 4.0 or later, or Subjects who swap to a D1 only dosing schedule)**

Assessments a	Baseline Screening b	Treatment Phase 21-day (3-week) Cycles Days			End of Treatment (EOT) Visit d	30 Day Follow-Up Visit (+/- 7 days)	Follow-up Q12W after last visit till study closes or withdrawal of consent – via phone call
		1	8	15 c			
Informed Consent	x						
Medical History/Demographics	x						
I/E Criteria	x						
HIV, HBV sAg, HBV cAb, HCV Ab	x						
Urinalysis	x	x			x		
TSH, T3, T4 e	x						
Optional Biomarker f	x						
Pregnancy Test g	x				x	x	
LVEF (echocardiogram or MUGA)	x					x	
12-lead electrocardiogram h	x	x h					
Physical Exam	x	x	x	x	x	x	
Vital Signs, height, and weight i	x	x	x	x	x	x	
Prior / Concomitant Medications and Procedures	x	x	x	x	x	x	
CBC/Differential	x	x	x	x	x	x	
Chemistry Panel	x	x	x	x	x	x	
Lipid Panel h	x h	x h					
Rapamycin level j		x j	x j	x j			
ECOG performance status	x	x	x	x	x	x	
CT k	x	Every 6 weeks for the first year, then every 12 weeks					
Nab-Sirolimus infusion l		x					
Pazopanib m		Daily					
Adverse Event Assessment		Continuous from time of consent to 30 days after last study drug					
Survival Assessment							x

a All visits are allowed to occur in a window of  $\pm 3$  days unless otherwise specified.

b Baseline screening visit will be done within 28 days prior to study treatment Day 1. Baseline scans should be completed within 28 days of C1D1, as close to C1D1 as possible.

c Day 15 visit is only in Cycle 1 and 2. Cycle 3+ does not have a Day 15 visit.

d End of Treatment-phase (EOT) Visit should be within  $\pm 3$  days of last study treatment.

e Thyroid function test to be repeated as needed, based on investigator's opinion.

f Subjects who consent for pre-treatment tissue collection for biomarker analysis: either fresh-frozen or formalin-fixed paraffin-embedded (FFPE) tumor blocks or unstained slides (min 10). Fresh tissue collection may only be obtained if clinically feasible and without undue risk to the subject.

g For all female subjects of childbearing potential (see Inclusion 5), a serum pregnancy test will be done at screening. A serum or urine pregnancy test will be repeated within 72 hours before first treatment if the serum pregnancy test occurred  $>72$  hours before dosing, and at EOT and 30-Day Follow-Up (if applicable). Pregnancy tests conducted after screening will be recorded in the source documentation only.

h Single tracing ECG and lipids evaluations are every even cycle (C2, C4, C6, etc.). Only lipid panel at baseline is required to be fasting lipid.

i Height is measured only at C1D1. BSA is calculated ONLY on C1D1; to be recalculated only if the weight changes by  $> 10\%$  in subsequent cycles, at which point the recalculated weight will become the new baseline. Vitals signs to include respiration rate, temperature, systolic/diastolic blood pressure, and pulse. Vital signs to be collected Pre-Dose (within 15 minutes prior to start of infusion) and Post-Dose (+10 minutes from end of infusion).

j Rapamycin levels are done locally and for all subjects in Phase 1 at Cycle 1 Day 1 Post-Dose (within +10 minutes from end of infusion), Cycle 1 Day 1 – 24-hour Post-Dose (optional, +/- 2 hours), Cycle 1 Day 8 and Day 15 anytime, as well as in Cycle 2 Day 1 Pre-Dose (within 15 minutes prior to infusion) and on Cycle 2 Day 8 and Day 15 (anytime).

k Baseline scans should be done within 4 weeks of C1D1, preferably as close to first treatment as possible. Every 6 weeks from C1D1 ( $\pm 1$  week) for the first year, then every 12 weeks (+/- 1 week) until disease progression or last treatment, regardless of missed or out of window doses. End of Treatment Visit CT/MRI should be performed only for those subjects that discontinue treatment for a reason other than disease progression. All responses must be confirmed by an additional CT scan after 6 weeks. MRI may be used if CT is contra-indicated for a subject. The same mode of imaging at screening must be used consistently throughout the study.

l Nab-Sirolimus must be administered after all study specific assessments are done in a visit. Pazopanib dosing is daily and oral and may be dosed anytime in relation to ABI-009 administration. Nursing supervision or documentation of pazopanib dosing on days where nab-Sirolimus is administered is not needed. See Section 6.2 for pazopanib dosing, schedule, and administration. Vital signs to be collected Pre-Dose (within 15 minutes prior to start of infusion) and Post-Dose (+10 minutes from end of infusion). There is a 60-minute observation window post end of infusion for Cycle 1. If a subject completes Cycle 1 with no infusion related reactions, the observation period may be omitted for Cycle 2 and onwards. If at any time the subject experiences an infusion related reaction, the 60-minute post-dose observation period will be reinstated.

m Subjects will complete daily drug diary when receiving pazopanib, to be reviewed on Day 1 of each cycle

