#### **5.2.4. Response Assessment**

Tumor response will be assessed by CT or MRI scan of the chest, abdomen, and pelvis (CAP) per institutional guidelines; image preparation and evaluation will follow the specifications provided in the RECIST version 1.1. The same modality (CT or MRI) must be used at screening and throughout the study.

CT/MRI scans to be performed at the following frequency:

- ≤4 weeks prior to C1D1 (as close to C1D1 as possible) (screening)
- Followed by every 6 weeks from C1D1 ( $\pm$  1 week) for the first year; then every 12 weeks ( $\pm$  1 week) until disease progression or unacceptable toxicity. End of Treatment Visit CT/MRI should be performed only for those subjects that discontinue treatment for a reason other than disease progression.

An unscheduled scan for suspected disease progression may be performed at any time. However, adherence to the planned imaging schedule is critical regardless of dose delays or unscheduled or missed assessments. Determination of disease progression for clinical management of subjects on study will be assessed at the local site. If an initial observation of objective response (CR or PR) is made, a confirmation scan should be done at 6 weeks after initial observation.

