#### **Endpoints in Phase 2 – Data from both phase 1 and 2**

##### **Primary Endpoint**

- Progression-free survival (PFS) rate at 3 months, based on Response Evaluation Criteria in Solid Tumors (RECIST) v1.1

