### **9.3. Efficacy Analysis**

Subjects will be evaluated for ORR, DCR, or progressive disease (PD) by CT imaging. Contrast enhanced MRI can also be used if CT is contra-indicated, as long as the same modality is used throughout the study. Baseline scan results can be accepted from outside institutions but must be done within 4 weeks of starting therapy and must include (as clinically indicated), chest abdominal, and pelvic CT or MRI. The first response assessment by CT or MRI scans documenting target lesions will be done 6 weeks after C1D1 and should be repeated every 6 weeks for the first year, then every 12 weeks thereafter until the end of treatment. If an initial observation of objective response (CR or PR) is made, a confirmation scan should be done at 6 weeks after initial observation. Scans should continue on schedule regardless of delays in nab-Sirolimus dosing.

The efficacy endpoints of ORR (CR + PR), DCR (CR, PR, and SD  $\geq 18$  weeks), and PFS will be determined by a local radiologic assessment using RECIST v1.1. After the 30-Day Follow Up Visit, subjects will be followed for survival every 12 weeks ( $\pm 3$  weeks), or more frequently as needed, until death, withdrawal of consent, or the study closes, whichever is the earliest.

The number and percentage of subjects achieving response ORR, DCR, or progressed will be summarized.

Median PFS and OS will be summarized using Kaplan-Meier (KM) analysis. Analysis of other efficacy endpoints, PFS rate at 3 and 6 months, and OS rate at 12 months will be assessed via descriptive statistics, for the number of subjects is expected to be small.

Response duration usually will be measured from the time of initial response until documented tumor progression.

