### **9.5. Sample Size Considerations**

**Phase 1:** Up to 49 subjects to identify the MTD, but the MTD may be reached with as few as 22 subjects. Subjects who discontinue from the study prior to completing the DLT assessment window for reasons other than toxicity will be replaced at the same dose level.

**Phase 2:** For sample size determination, we assume the following:

1. For aa-TKI/pazopanib monotherapy in nonadipocytic STS, the baseline anticipated PFS rate at 3 months is approximately 50%.
2. An increase by the combination therapy of the PFS rate at 3 months to 70% would be considered clinically meaningful.
3. This is an exploratory phase 1/2 study. Thus, type I (false positive) errors are less worrisome than type II (false negative). We therefore set alpha=0.1 for rejection of null hypothesis. Beta is set at 0.1 (90% power), again, to minimize type II errors.
4. We are using a Simon's two-stage study design for the phase 2 efficacy evaluation.

In the first stage, at least 23 subjects would be enrolled, including the 3-6 subjects from phase 1 at the RP2D. If at least 11 were progression-free at the 3 months evaluation, then additional subjects would be enrolled to a total of 39 subjects in Phase 2. If at least 23 were progression-free at 3 months, then this would provide preliminary data to indicate that the combination was active and worthy of further evaluation in this clinical setting.

Subjects who fail to become evaluable for the secondary endpoint with a follow-up CT/MRI will be replaced.

To assess the primary endpoint, we elected to use a Simon's minimax design. This was selected to be most conservative in evaluable subjects needed to answer the primary hypothesis. In this case, a total of 39 evaluable subjects will be required in the phase II component of the study, if it extends through both stages.

This type of design has greater statistical power than a single-arm design. For example, a single arm trial enrolling the same number of subjects (n=39) would only have a statistical power of 82%, versus 90% for the proposed design. Alternatively, it would require 50 evaluable subjects in a single-arm design to achieve the desired 90% power.

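### The plan has no rule for counting subjects with unknown RECIST status at 3 months, and its evaluable set and replacement rule can remove likely failures from the primary PFS rate

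*Combined protocol and SAP*

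**What the plan says.** The phase 2 primary endpoint in Section 9.1 is "Progression-free survival (PFS) rate at 3 months, based on Response Evaluation Criteria in Solid Tumors (RECIST) v1.1". Section 9.5 scores it as a count in a Simon two-stage design: 23 subjects in stage 1 (continue with 11 or more progression-free) and 39 in total (active with 23 or more).

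Three passages say when scheduled imaging ends:

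- Footnote k to Tables 4 and 5: "until disease progression or last treatment, regardless of missed or out of window doses".
- Section 5.2.4: "until disease progression or unacceptable toxicity".
- Section 9.3: every 6 weeks in year 1, "then every 12 weeks thereafter until the end of treatment".

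Sections 2.4 and 5.6 limit later follow-up to survival and new anticancer therapy, by record review or telephone.

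A subject who stops for a reason other than progression has one End of Treatment scan. Footnote k and Section 5.2.4 exempt anyone stopped for disease progression. Section 5.3 exempts only RECIST progression. The synopsis lets therapy end for clinical progression.

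The definitions table counts progression or death from any cause as a PFS event. It defines a treated set (1 or more doses), a per-protocol set, and an efficacy set (measurable disease, 2 or more nab-sirolimus doses, a follow-up scan). It assigns none of them to the primary endpoint. Section 9.5 adds: "Subjects who fail to become evaluable for the secondary endpoint with a follow-up CT/MRI will be replaced".

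**The concern.** Early stopping for toxicity or clinical decline is unlikely to be independent of progression. If such subjects leave the count, or are replaced by others who reach a scan, the 3-month rate describes those who did well enough to be scanned. It is then compared with a 50% benchmark meant for the whole treated population.

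At stake are the stage 1 decision and the final claim of activity, which rest on counts among 23 and 39 subjects. A rule chosen after the data are seen could settle either one. On Day 1-only dosing the second dose comes at week 3 at the earliest, so a subject stopped by first-cycle toxicity is outside the efficacy set.

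**Working it through.** **Who is affected.** With scans every 6 weeks, ±1 week, I take the week-12 scan as the 3-month evaluation; the plan does not name the scan. Four groups of early stoppers follow from the text:

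1. Died, or progressed on the End of Treatment scan, by 3 months: a known event.
2. Two or more doses, End of Treatment scan clean and before the week-12 window, alive at 3 months: in the efficacy set and not replaced, but status unknown and no counting rule.
3. Fewer than 2 doses, with a follow-up scan: outside the efficacy set.
4. No follow-up scan: outside the efficacy set and replaced.

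**Inputs (Section 9.5).** Null rate 0.50: "the baseline anticipated PFS rate at 3 months is approximately 50" per cent. Target rate 0.70. "We therefore set alpha=0.1 for rejection of null hypothesis". "Beta is set at 0.1 (90% power), again, to minimize type II errors". Stage 1 n = 23, total n = 39. The test is taken as one-sided.

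**Reproducing the design.** With a1 and a the smallest passing counts at stage 1 and at the end,

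P(active | p) = Σ over x from a1 to 23 of Bin(x; 23, p) × P[Bin(16, p) ≥ a − x].

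- A minimax search gives n = 39 with 23 in stage 1, continue at ≥12, active at ≥24: P(active | 0.50) = 0.098 and P(active | 0.70) = 0.902. This matches the stated sample size and error rates.
- The cut-offs as written (≥11, ≥23) give 0.167 and 0.949. That mismatch is a separate matter; both sets are carried below.

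**Effect of removing subjects.** Assume a share m is excluded or replaced, their true 3-month PFS rate is r, and the true all-treated rate is 0.50. The rate among those counted is p_e = (0.50 − m·r)/(1 − m). For m = 10%:

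- r = 0: 0.50/0.90 = 0.556
- r = 25%: 0.475/0.90 = 0.528
- r = 50%: 0.45/0.90 = 0.500

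False-positive rate, cut-offs ≥12/≥24, with the written cut-offs in brackets:

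| m | r = 50% | r = 25% | r = 0% |
|---|---|---|---|
| 5% | 0.098 [0.167] | 0.13 [0.21] | 0.17 [0.26] |
| 10% | 0.098 [0.167] | 0.17 [0.27] | 0.27 [0.39] |
| 15% | 0.098 [0.167] | 0.23 [0.34] | 0.43 [0.56] |

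**Effect of other rules at m = 10%.**

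- Unknown counted as progression-free: the counted rate under the null is 0.50 − m·r + m, which is 0.55 (r = 50%) to 0.60 (r = 0). The false-positive rate is 0.252 to 0.485 with ≥12/≥24.
- Unknown counted as not progression-free: the counted rate is the true rate minus m·r, so the false-positive rate does not exceed 0.098. At a true rate of 0.70 the counted rate is 0.700, 0.675 or 0.650 for r = 0, 25% or 50%, and power is 0.90, 0.83 or 0.73.

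**The case against.** A reader might infer that every early stopper lacks a 3-month status. The documents do not support that. Deaths are events, the End of Treatment scan can show progression, and a stop in week 11 can place that scan inside the week-12 window.

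A reader might also infer that clinical progressors are dropped. The PFS definition refers to disease progression without limiting it to RECIST, so they may count as failures. Section 5.3 would still have them scanned, and Section 5.2.4 allows an unscheduled scan for suspected progression. What the text shows is a conflict and an undefined event status, not established exclusion.

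Nor does the text establish that the primary rate must come from a selected group. No passage ties the endpoint to the efficacy set, the replacement sentence speaks of the secondary endpoint, and a toxicity stopper with 2 doses and a clean End of Treatment scan is neither replaced nor outside that set.

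Finally, 3 of the first 13 subjects (23%) stopped for adverse events, but these were closed Day 1/Day 8 cohorts and stops at any time on treatment. That figure is only illustrative and is not a before-month-3 rate at the recommended phase 2 dose.

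These objections limit the size and reach of the problem. They leave two things untouched: no rule covers the unknown-status subject, and the only rules written down on evaluability (the efficacy set, the replacement sentence, and Section 9.5's requirement for 39 evaluable subjects) point toward exclusion.

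**Conclusion.** The point holds in this form: scheduled imaging ends with treatment, an early stopper without progression can be alive with no RECIST status at 3 months, and the plan neither says how that subject counts nor names the primary analysis set. If the efficacy set and replacement rule are applied to the primary endpoint, likely failures leave the denominator.

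The size is a range. With 5% to 15% of subjects removed, the false-positive rate under the minimax cut-offs runs from 0.098 (no inflation, removed subjects as good as the rest) to 0.43 (15% removed, all true failures). With the written cut-offs it runs from 0.167 to 0.56. The upper ends are worst cases. The removed share and the outcome of those removed are assumptions, because the documents give neither. The direction of any bias depends on the missing rule.

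**What to change.** In Sections 9.3 and 9.5 state, before the stage 1 decision:

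- The primary analysis includes every treated subject at the recommended phase 2 dose, with no replacement for this endpoint.
- Death or progression by 3 months, including documented clinical progression, is a failure.
- A scan without progression at week 11 or later (week 12 minus the 1-week window) makes the subject progression-free at 3 months, even if the week-12 scan was missed or late.
- Any other unknown status counts as not progression-free. Report an evaluable-only or Kaplan-Meier estimate as a sensitivity analysis; the latter needs a censoring rule, which the plan lacks.

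Reconcile the imaging stop points in footnote k (Tables 4 and 5), Section 5.2.4 and Section 9.3. Reconcile the End of Treatment scan exemption in footnote k and Section 5.2.4 with Section 5.3. For subjects who stop without progression, use scans from the existing schedule or standard of care, at least through the 3-month assessment.

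The counting rule costs only wording, with no added scans. Dropping replacement adds no patients. The rule guards against upward bias but is conservative: the reported rate will be less favourable, and with 10% affected and a true rate of 70%, power falls from 0.90 to 0.83 or 0.73 if 25% or 50% of those subjects are truly progression-free. Obtaining the 3-month scan where possible limits that loss.
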